6.9.5 Bleeding Events

Bleeding events are AESIs and considered an important identified risk for bintrafusp alfa (refer to the IB).

6.9.5.1 Mucosal/Non-Tumor Bleeding

Participants treated with bintrafusp alfa were commonly reported with mild to moderate mucosal AEs such as epistaxis, hemoptysis, gingival bleeding and hematuria. In general, these reactions resolve without discontinuation of treatment.

For Grade 2 non-tumor bleeding, see Section 6.8 for general management of Grade 2 treatment-related TEAEs.

For Grade 3 non-tumor bleeding, study intervention must be permanently discontinued unless an alternative explanation can be identified (such as concomitant use of antithrombotic agents, traumatic event, etc.). In case of alternative explanations for the Grade 3 bleeding event, study intervention should be held until the event recovers to Grade ≤ 1 .

For Grade 4 non-tumor bleeding, treatment must be permanently discontinued if no alternative explanation is identified.

6.9.5.2 Tumor Bleeding

Participants treated with bintrafusp alfa were reported in lower frequencies, with Grade ≥ 3 hemorrhages including tumor bleeding. For Grade ≥ 2 tumor bleeding, study intervention must be held until the event recovers to Grade ≤ 1 . Treatment should be permanently discontinued if the Investigator considers the participant to be at risk for additional severe bleeding.

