6.8 Special Precautions

Any treatment-emergent adverse event (TEAE) that is assessed as potentially related to bintrafusp alfa, may require permanent or transient discontinuation of bintrafusp alfa treatment.

Single laboratory values out of the normal range that do not have any clinical correlation do not necessarily need treatment interruption. Questions or concerns with regard to management and/or follow-up of TEAEs should be discussed with the Medical Monitor.

Immune-related AEs, IRRs including hypersensitivity, anemia, TGF- β inhibition mediated skin reactions, and bleeding events are managed and followed up in their respective sections as indicated below. Permanent study intervention discontinuation may be recommended, so the relevant section must be reviewed:

- For suspected irAEs, general management by NCI-CTCAE v5.0 toxicity grading is listed in Section [6.9.2](#). Recommended guidance and management for specific irAEs as per published guidelines is provided in [Appendix 5](#).
- IRR and hypersensitivity reaction guidance are presented in Section [6.9.1](#).
- Anemia guidance is presented in Section [6.9.4](#).

- Potential TGF- β inhibition mediated skin AEs guidance and management are provided in Section **Error! Reference source not found..**
- Guidance and management of bleeding events are discussed in Section **6.9.5.**

General guidance:

- In any case, if ≥ 2 doses are missed due to AE, the Medical Monitor should be consulted.
- Inability to reduce corticosteroid dose to 10 mg or less of prednisone or equivalent per day within 12 weeks is an indication for permanent treatment discontinuation (except for use of steroids as hormone substitution).
- Persistent Grade 2 or 3 adverse reactions (excluding endocrinopathies controlled with hormone replacement therapy) that do not recover to Grade 0 to 1 within 12 weeks after last dose of study intervention is an indication for permanent treatment discontinuation.

In general, the following applies for TEAEs related to bintrafusp alfa that are not covered by the recommendations for irAE management in [Appendix 5](#):

Grade 4 treatment-related TEAEs

Any Grade 4 treatment-related TEAEs require permanent treatment discontinuation, except:

- Endocrinopathies that have been controlled by hormone replacement,

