- Isolated laboratory values out of normal range that do not have any clinical correlation. Discuss with Medical Monitor regarding work-up, management, and treatment continuation versus hold versus discontinuation for isolated Grade 4 laboratory abnormalities
- If alternative explanation is identified for Grade 4 non-tumor bleeding.

See [Appendix 5](#) for guidance on specific Grade 4 irAEs, as most require permanent treatment discontinuation.

Grade 3 treatment-related TEAEs

1. Participants with any severe or Grade 3 treatment-related adverse reactions that recur should be permanently discontinued. Exceptions may be considered for the following after discussion with Medical Monitor:

- Transient Grade 3 flu-like symptoms or fever that is controlled with medical management
- Transient Grade 3 fatigue, local reactions, headache, nausea, emesis that resolves to \leq Grade 1 or baseline
- Tumor flare phenomenon defined as local pain, irritation, or rash localized at sites of known or suspected tumors
- Any Grade ≥ 3 drug-related amylase or lipase abnormality that is not associated with symptoms or clinical manifestations of pancreatitis

- Grade 3 Hgb decrease (< 8.0 g/dL) that is clinically manageable with blood transfusions or erythroid growth factor use
- Increases in ECOG PS ≥ 3 that resolves to ≤ 2 by Day 1 of the next infusion (i.e., infusions should not be given if the ECOG PS is ≥ 3 on the day of treatment and should be delayed until ECOG PS ≤ 2)
- KA and cutaneous squamous cell carcinoma (cSCC)
- Grade 3 non-tumor bleeding requiring intervention or hospitalization if alternative explanation can be identified (such as concomitant use of antithrombotic agents, traumatic event, etc).

2. See [Appendix 5](#) for guidance on specific Grade 3 irAEs as many require permanent treatment discontinuation, including pneumonitis and nephritis.
 - AST or ALT > 5 times ULN or total bilirubin > 3 times ULN must be permanently discontinued, except for participants with liver metastases (e.g., who begin treatment with Grade 2 AST or ALT). These participants should be discontinued if AST or ALT increases by $\geq 50\%$ relative to baseline and lasts for at least 1 week.
3. Persistent Grade 3 adverse reactions (excluding endocrinopathies controlled with hormone replacement therapy) that do not recover to Grade 0 to 1 within 12 weeks after last dose of treatment.

Grade 2 treatment-related TEAEs

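### Protocol 6.8 and 6.9.5.2 give different stopping instructions for treatment-related tumor bleeding, and no section states a hold for an explained Grade 4 non-tumor bleed

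*Protocol*

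**What the plan says.** **Section 6.8, Grade 4.** "Any Grade 4 treatment-related TEAEs require permanent treatment discontinuation, except" for a short list. The one entry on bleeding reads: "If alternative explanation is identified for Grade 4 non-tumor bleeding". Tumor bleeding is not listed.

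**Section 6.8, Grade 3, item 1.** "Participants with any severe or Grade 3 treatment-related adverse reactions that recur should be permanently discontinued". Exceptions may be considered after discussion with the Medical Monitor. The only one that concerns bleeding is again non-tumor bleeding with an identifiable alternative explanation.

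**Section 6.8, scope.** The grade rules are introduced by "In general, the following applies for TEAEs related to bintrafusp alfa that are not covered by the recommendations for irAE management in" Appendix 5. Earlier in 6.8, bleeding is referred to 6.9.5 for guidance.

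**Section 6.9.5.1, non-tumor bleeding.** An unexplained Grade 3 bleed is a permanent stop. For an explained one, "In case of alternative explanations for the Grade 3 bleeding event, study intervention should be held until the event recovers to Grade" 1 or lower. For the next grade up: "For Grade 4 non-tumor bleeding, treatment must be permanently discontinued if no alternative explanation is identified". Nothing follows for the explained Grade 4 case.

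**Section 6.9.5.2, tumor bleeding.** From Grade 2 upward, drug is held until Grade 1 or lower. The permanent stop is conditional: "Treatment should be permanently discontinued if the Investigator considers the participant to be at risk for additional severe bleeding". The section draws no line by relatedness and none between Grades 2, 3 and 4.

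**The concern.** A site with a severe bleed in front of it will look in 6.8 for the rule by grade and in 6.9.5 for the rule by event. For treatment-related tumor bleeding these need not agree. One section fixes the permanent stop by grade or recurrence, and the other makes it depend on the Investigator's view of future risk.

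The current amendment raised bleeding to an important identified risk, and 6.9.5.2 acknowledges that hemorrhages of Grade 3 or higher, including tumor bleeding, have been reported. Infusions are scheduled every 2 weeks, so on schedule the decision falls due within 14 days of the event. Participant safety is the main stake.

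There is also a data consequence. SAP 15.1.2 separates events leading to temporary interruption from those leading to permanent discontinuation. If two sites follow different sections, the same clinical event lands in different categories, and it is unclear which site has deviated from the protocol.

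**Working it through.** No arithmetic applies, and the plan states no figure to reproduce. The check sets the sections side by side by bleeding type, grade, relatedness and alternative explanation.

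| Situation | 6.8 | 6.9.5.1 or 6.9.5.2 | Result |
|---|---|---|---|
| Grade 4 tumor, treatment-related | Permanent stop, no exception | Hold to Grade ≤ 1; permanent stop if judged at further risk | Conflict |
| Grade 4 tumor, unrelated | Grade 4 rule does not apply | As above | No conflict |
| Recurrent Grade 3 tumor, treatment-related | Permanent stop, no tumor-bleeding exception | As above | Conflict |
| Grade 4 non-tumor, explained | Exempt from the permanent stop; no hold stated | Permanent stop only if unexplained; no hold stated | Gap |
| Grade 4 non-tumor, unexplained | Permanent stop if treatment-related | Permanent stop | No conflict |
| Grade 3 non-tumor, explained | Exception to the recurrence rule may be considered | Hold to Grade ≤ 1 | Compatible |
| Grade 3 non-tumor, unexplained, first event | Item 1 speaks only to recurrence | Permanent stop | Compatible |

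**When the conflict bites.** In the two conflict rows, both sections end in a permanent stop if the Investigator sees a risk of further severe bleeding. They part when the event has recovered to Grade 1 or lower and the Investigator sees no such risk. Then 6.9.5.2 gives no reason for a permanent stop, while 6.8 still calls for one.

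**Is precedence stated?** Three places might settle it, and none does.

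1. The introduction to the grade rules in 6.8 carves out events covered by the irAE recommendations in Appendix 5. It does not carve out 6.9.5.
2. 6.8 refers bleeding to 6.9.5 but also writes its own bleeding exceptions at Grades 3 and 4. Both are for non-tumor bleeding. If bleeding were wholly outside these rules, the exceptions would not be needed.
3. Section 7.1 sends the reader to both 6.8 and 6.9 for events requiring discontinuation, with no ranking.

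**The gap row.** 6.8 and 6.9.5.1 agree that an explained Grade 4 non-tumor bleed is not a mandatory permanent stop. Neither goes on to state a hold or a recovery grade. Two other parts of the protocol do not fill this:

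- The 12-week non-recovery rule in 6.8 names Grades 2 and 3 only.
- Appendix 4 requires a reasonable alternative explanation before an event is called unrelated, so an explained bleed may well be assessed as unrelated. It then falls outside the treatment-related rules of 6.8, leaving only 6.9.5.1, which is silent on this case.

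**The case against.** The best defense is that the specific section governs. 6.8 says bleeding is managed in its own section, tells the reader to review that section, and opens its grade rules as general ones. Moreover, 6.9.5.2 does not order a restart after Grade 4, so a site that stops permanently for a treatment-related Grade 4 tumor bleed complies with both sections. These arguments narrow the point but do not remove it. A site that resumes under 6.9.5.2 still departs from 6.8, and no text ranks the two.

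Three stronger readings are tempting, and the documents do not support them.

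- **That every Grade 4 tumor bleed is caught in the conflict.** The 6.8 rule covers treatment-related events only. For an unrelated bleed, 6.9.5.2 stands alone.
- **That explained Grade 4 non-tumor bleeding is a contradiction, or that such a participant would simply be dosed on schedule.** The two sections agree as far as they go; text is missing. Other safeguards also apply: immediate safety concerns go to the Sponsor (Section 8), a clinical Grade 4 event must be reported as an SAE within 24 hours (Appendix 4), and the Investigator may stop treatment for safety at any time (7.1). None is a bleeding-specific hold, but unsupervised dosing is speculation. Antithrombotic use is given as an example of an alternative explanation only in the Grade 3 text.
- **That 6.8 and 6.9.5.1 conflict on a first unexplained Grade 3 non-tumor bleed.** Item 1 of 6.8 says that recurring reactions should lead to a permanent stop. It does not say that only recurring ones do, and items 2 and 3 add further Grade 3 stops. The first-event rule in 6.9.5.1 fits beside it.

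Finally, SAP 4.1 records that the study was stopped early with few participants and no efficacy analysis. That limits practical exposure but does not make the text consistent.

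**Conclusion.** The point holds in a limited form. Two situations receive different instructions without stated precedence: treatment-related Grade 4 tumor bleeding and recurrent treatment-related Grade 3 tumor bleeding, in each case when the bleed has recovered and the Investigator sees no further severe-bleeding risk. One situation, an explained Grade 4 non-tumor bleed, lacks a stated hold or recovery condition.

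This rests on reading the grade rules in 6.8 as applying to bleeding. Its own bleeding exceptions support that reading, but no sentence says so outright. The number of participants affected cannot be estimated, because the documents give no rate for bleeding by grade or type. Which instruction is clinically right is not judged here.

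**What to change.** Reconcile 6.8 (the Grade 4 exceptions, and Grade 3 item 1 with its bleeding exception) with 6.9.5.1 and 6.9.5.2. The clearest form is one table by bleeding type, grade (2 to 4), relatedness and alternative explanation, with one instruction per cell. 6.8 would cross-refer to the table and no longer restate bleeding rules. A lighter alternative is a sentence saying which section prevails, plus an explicit instruction for the explained Grade 4 non-tumor case. The content of every cell is for the sponsor's medical team.

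The cost is one small table or a few sentences in a protocol amendment, with no new procedures or data collection. As the study has been discontinued early, the main use may be in any other bintrafusp alfa protocol that carries the same text; whether one does is an assumption these documents cannot confirm.

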6.9.6 Other Potential Risks

6.9.6.1 Impaired Wound Healing

Impaired wound healing is considered an important potential risk (a theoretical risk-based on literature findings) for bintrafusp alfa, given the role of TGF- β in wound healing. Management should be discussed with the Medical Monitor for participants requiring surgery during the study. It is recommended to hold study intervention for approximately 4 weeks after major surgery for observation. Postoperative wound healing will be closely monitored.

6.9.6.2 Embryofetal Toxicity

Embryofetal toxicities are a known risk of the PD-1/PD-L1 targeting class and are considered important potential risks for bintrafusp alfa. Animal models link the PD-1/PD-L1 signaling pathway with maintenance of pregnancy through induction of maternal immune tolerance to fetal tissue. An appropriate contraception warning is provided as part of the inclusion criteria. Pregnant and breastfeeding women are not allowed in the bintrafusp alfa study, and adequate contraceptive measures are recommended during the study to minimize or eliminate the potential risk to the developing fetus.

Respective safety measures comprise of inclusion/exclusion criteria for participation in clinical studies with bintrafusp alfa, guidance for prevention, monitoring, and medical management of potential risks, as well as guidance on study intervention interruption or discontinuation.

7**Discontinuation of Study Intervention and Participant Discontinuation/Withdrawal****7.1****Discontinuation of Study Intervention**

Participants may be discontinued from study intervention for any of the following reasons, one reinitiating course of treatment may be allowed (see Section 7.1.2.1).

- A participant may discontinue from the study intervention at any time at his/her own request (i.e., withdrawal of consent), and without giving a reason.
- Occurrence of an exclusion criterion, which is clinically relevant and affects the participant's safety, if discontinuation is considered necessary by the Investigator and/or Sponsor.
- A participant may be discontinued at any time at the discretion of the Investigator for safety, behavioral, compliance, or administrative reasons (See Section 6.8 and Section 6.9 for TEAEs and AESIs that require treatment discontinuation, respectively).
- PD per RECIST 1.1 plus subsequent confirmation (repeat imaging 4 to 6 weeks after initial determination of PD), with the exception that participants receiving treatment may continue past PD if the participant's ECOG PS has remained at least stable, and, if in the opinion of the Investigator, the participant may benefit from continued treatment (see Section 7.1.3). A participant with significant symptomatic disease progression and/or clinical deterioration should be discontinued prior to confirmation of PD per RECIST 1.1.
- Unacceptable toxicity
- Some TEAEs and AESIs require withdrawal from treatment. See Section 6.8 and Section 6.9 for additional details.
- Drug must not be given to a known pregnant participant (see Appendix 3).
- Use of a prohibited concomitant drug, as defined in Section 6.5.2, where the predefined consequence is withdrawal from the study intervention.

In case of discontinuation from the study intervention:

- The day of End-of-Treatment Visit will correspond to the day of withdrawal (or within 7 days).
- An attempt should be made to perform all assessments scheduled for the End-of-Treatment Visit if possible. If not possible, the most clinically relevant assessments and appropriate eCRFs for the End-of-Treatment Visit should be prioritized as feasible.
- Participants will be asked to continue Safety Follow-up and Survival Follow-up, which includes the collection of data on survival, and subsequent anticancer therapy. After completion of the follow-up period or after the End-of-Treatment Visit, whichever is applicable, the appropriate eCRF section for Study Termination must be completed.
- If the participant is enrolled into a new study or any new therapy post-withdrawal from study intervention, the Safety Follow-up Visit should be scheduled prior to the start of the new treatment irrespective of the 28-day Safety Follow-up period.

The Schedule of Activities specifies the data to collect at study intervention discontinuation and follow-up, and any additional evaluations that need to be completed.

7.1.1 **Temporary Discontinuation**

See Section 6.8 and Section 6.9 for guidance on temporary discontinuation from study intervention.

7.1.2 **Rechallenge**

7.1.2.1 **Reinitiation**

One reinitiating course of treatment at the same dose and schedule and treatment duration up to 24 months is allowed at the discretion of the Investigator and agreement of the Medical Responsible for:

- Participants who are experiencing SD, PR, or CR at the time of discontinuation, and then subsequently develop disease progression after stopping therapy, but prior to the End of the Study.

OR

- Participants who are discontinued due to an AE that are subsequently well managed or resolved after stopping therapy, but prior to the End of the Study.

The participant should reinitiate treatment at the treatment phase visit where they left off according to the Schedule of Activities (Table 1). Participants who reinitiate treatment should stay on study and should be treated and monitored according the Schedule of Activities for the rest of the study.

Prior to reinitiation, the Investigator will need to confirm that the benefit of reinitiating treatment outweighs any risk involved, such as that which led to initial treatment discontinuation. For participants with only SD at the time of discontinuation, the Investigator should confirm that no other reasonable treatment options are available. In addition, to be eligible for reinitiation, the participant must not have previously withdrawn consent for this study and should have been followed up with regular eCRF documented evaluation scans up to reinitiation of treatment.

A new baseline scan must be performed prior to reinitiation of study intervention. Additionally, relevant safety laboratory assessments, including both full hematology and full chemistry results within 2 weeks, must be available and verified. The clinical Investigator will determine whether additional evaluation and work-up are required on a case-by-case basis. A discussion with the study team is warranted to determine whether PK/biomarker testing is indicated upon restarting treatment.

7.1.3

Treatment Beyond Progression

7.1.3.1

Treatment Beyond Initial Progression

Participants will receive bintrafusp alfa as outlined in the Schedule of Activities until disease progression. Bintrafusp alfa may continue past the initial determination of disease progression according to RECIST v1.1 as long as the following criteria are met:

- Treatment with bintrafusp alfa is ongoing.
- No new unacceptable treatment or disease-related toxicity.
- Tolerance of study interventions.
- At least stable ECOG PS.
- Treatment beyond progression will not delay an imminent intervention to prevent serious complications of disease progression (e.g., CNS metastases).

A radiographic assessment should be performed within 4 to 6 weeks of original PD to determine whether there has been a decrease in the tumor size, or continued PD. The assessment of clinical benefit should be balanced by clinical judgment as to whether the participant is clinically deteriorating and unlikely to receive any benefit from continued treatment with bintrafusp alfa.

7.1.3.2

Treatment Beyond Confirmed Progression

After confirmed PD, if the Investigator feels that the participant continues to achieve clinical benefit by continuing treatment, the participant should remain on the study and continue to receive monitoring according to the Schedule of Activities. The decision to continue treatment beyond confirmed PD should be discussed with the Medical Monitor and documented in the study records.

Participants who continue beyond progression will be evaluated for further tumor response as per the protocol schedule. Treatment should be discontinued permanently upon documentation of further, unequivocal, disease progression unless there are no alternative therapeutic options and the benefit-risk assessment is favorable in consultation between the Investigator and the Medical Monitor. In case of continuation of treatment beyond PD, treatment will be discontinued once any other criteria for withdrawal are met.

7.1.3.3

Continuation of Study Intervention After Local Treatment of Disease Progression

If disease progression is due to brain metastasis, participants may continue study interventions after the local treatment of the brain lesions provided that the above criteria are met in addition to the following:

- Tumor assessment showing disease progression has been performed and was documented according to RECIST 1.1 prior to the procedure.
- Brain metastases have been treated locally and are clinically stable for at least 2 weeks prior to reinitiation of study interventions.

- There are no ongoing neurological symptoms that are related to the brain localization of the disease (sequelae that are a consequence of the treatment of the brain metastases are acceptable).
- Participants must be either off steroids or on a stable or decreasing dose of ≤ 10 mg daily prednisone (or equivalent).
- Benefit-risk assessment to continue study intervention is favorable under consideration of any alternative treatment options as assessed by the Investigator.

In addition, if disease progression is mainly due to a metastatic lesion which in the opinion of the Investigator may be surgically removed, participants may continue study interventions after the local treatment of such a lesion provided that:

- Tumor assessment showing disease progression has been performed and was documented according to RECIST 1.1. prior to the procedure.
- It has been at least 2 weeks and the participant has fully recovered from the surgery.
- Benefit-risk assessment to continue study intervention is favorable under consideration of any alternative treatment options as assessed by the Investigator.

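### Protocol Section 7.1.2.1 allows reinitiation after an AE that is later managed or resolved and does not carve out AEs for which the protocol requires permanent, or mandates, discontinuation

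*Protocol*

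**What the plan says.** Section 7.1 of the Protocol opens its list of reasons for stopping treatment with "Participants may be discontinued from study intervention for any of the following reasons, one reinitiating course of treatment may be allowed" and refers to Section 7.1.2.1. One item in that list reads "Some TEAEs and AESIs require withdrawal from treatment" and points to Sections 6.8 and 6.9.

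Section 7.1.2.1 then says that one course at the same dose and schedule, for up to 24 months, "is allowed at the discretion of the Investigator and agreement of the Medical Responsible for" two groups. The first is participants with disease control at discontinuation who progress later. The second is "Participants who are discontinued due to an AE that are subsequently well managed or resolved after stopping therapy", provided this happens before the end of the study. The Investigator must confirm that "the benefit of reinitiating treatment outweighs any risk involved, such as that which led to initial treatment discontinuation". Full hematology and chemistry results from the last 2 weeks and a new baseline scan are compulsory. One group is expressly shut out: "to be eligible for reinitiation, the participant must not have previously withdrawn consent for this study". Regular documented scans up to reinitiation are also expected.

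Section 6.8 says that related events "may require permanent or transient discontinuation of bintrafusp alfa treatment", and then sets firm rules, for example "Any Grade 4 treatment-related TEAEs require permanent treatment discontinuation, except", followed by three exceptions. Section 6.9 and Appendix 5 add further firm rules.

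The SAP, in its definition of the on-treatment period (Section 9.8), defers to the Protocol's rules on reinitiation and adds no restriction.

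**The concern.** A rule that requires permanent discontinuation exists to take the re-dosing decision out of case-by-case judgment. Section 7.1.2.1 hands that decision back to the Investigator and the Medical Responsible for any AE discontinuation, and its threshold is low: the event need not have resolved, since being well managed is enough. Re-dosing is at the full dose, because Section 6.6 allows no dose modification.

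If the two sets of rules are not ranked, a site could rely on Section 7.1.2.1 to restart bintrafusp alfa after, say, a Grade 4 immune-related event or a Grade 3 infusion-related reaction. At stake is the safety of the individual participant.

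**Working it through.** No arithmetic applies; the check is a comparison of texts.

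**Step 1. Which stops are firm?** Only wording that requires, mandates or says must is taken.

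| Event | Place in the Protocol | Stop |
|---|---|---|
| Grade 4 treatment-related TEAEs not covered by Appendix 5, outside the three exceptions | 6.8 | permanent |
| AST or ALT above 5 times ULN, or bilirubin above 3 times ULN, without liver metastases | 6.8 | permanent |
| Grade 3 pneumonitis and Grade 3 nephritis | 6.8, with Appendix 5 Tables A3 and A6 | permanent |
| Listed Grade 4 irAEs (for example rash, nephritis, aplastic anemia) | 6.9.2; most repeated in the Appendix 5 introduction | permanent |
| Grade 3 or 4 non-tumor bleeding without an alternative explanation | 6.9.5.1 | permanent |
| Grade 3 or 4 infusion-related reactions | notes to Table 5 in 6.9.1 | mandated |

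The rows are not a tally of separate rules. Grade 4 non-tumor bleeding, for instance, is also within the first row's rule, whose exceptions name it.

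**Step 2. Does Section 7.1.2.1 reach participants stopped under these rules?** On its words, yes. Temporary holds have their own section, 7.1.1. Section 7.1.2.1 stands under the title of rechallenge and concerns participants who have stopped therapy. A participant stopped for a Grade 4 event that later resolves fits the second group literally.

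**Step 3. Does any text exclude them?** The one express bar is withdrawn consent. No cross-reference to Section 6.8, Section 6.9 or Appendix 5 limits the second group. The Section 7.1 lead-in goes the other way, since its list contains the TEAEs and AESIs with a required withdrawal.

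**Step 4. Does the Protocol rank the rules elsewhere?** Section 8 allows no waivers or exemptions, but a course given under Section 7.1.2.1 would be a use of the Protocol, not a waiver of it. By contrast, Section 7.1.3.1 makes the absence of new unacceptable toxicity a condition for treatment beyond initial progression, and Section 7.1.3.2 says that treatment beyond progression ends once any other withdrawal criterion is met. Section 7.1.2.1 has no matching clause.

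**Step 5. Does Appendix 5 settle it?** Not for Guillain-Barré syndrome. Table A7 instructs permanent discontinuation at Grades 3 and 4, which it labels severe, and then advises only caution about rechallenge in severe cases. That remark may be carried over from the source guideline, but a site reads it as part of the Protocol.

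**The case against.** The best answer is that permanent means not restarted. Section 6.8 itself contrasts permanent with transient discontinuation. Section 7.1.2.1 only permits, while the stops require, and a general permission does not naturally override a specific prohibition. The AE group keeps a meaning of its own, because Section 7.1 also allows discretionary stops for safety that no permanent rule covers. A site that never re-doses complies with everything.

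The lead-in is weak evidence of a contrary intent. Taken literally it would also cover withdrawn consent, which Section 7.1.2.1 bars, and pregnancy, in which the drug must not be given. For infusion-related reactions, Table 5 says to resume without the causal drug, which in a monotherapy study leaves nothing to restart.

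The safeguards are also more than the Investigator's opinion. The Medical Responsible is a second party, and the laboratory results are a fixed requirement. Exclusion criterion 2 (pneumonitis that needed oral or intravenous steroids) and criterion 7 (Grade 3 or higher hypersensitivity to bintrafusp alfa) bear on re-dosing through the second bullet of Section 7.1, although that bullet applies only if the Investigator or Sponsor considers discontinuation necessary.

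Most of this stands as a reading of intent. It does not supply the missing sentence. The argument from the word permanent does not reach the infusion-reaction rule on its wording, and the safeguards either turn on judgment or, like the laboratory results, do not ask which rule caused the stop.

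Two stronger readings are tempting. A reader might infer that the Protocol intends re-dosing after required stops; the texts above make that unlikely. A reader might also cite the caution about rechallenge under myositis in Table A5 as a second contradiction. It is not one: Grade 3 myositis is normally held until it improves and Grade 2 can be held and resumed, so the remark has an obvious target other than the permanent Grade 4 stop.

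**Conclusion.** The point holds as an unresolved conflict between two stated rules on patient safety, and it should be fixed. As written, Section 7.1.2.1 with the Section 7.1 lead-in permits one full-dose course after any AE discontinuation once the AE is managed or resolved, and none of the firm stops in the table is expressly excluded.

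The conclusion rests on the absence of any ranking text in the Protocol or SAP, which is certain for the text available. It does not rest on a view that the sponsor wants such re-dosing, or that anyone was harmed. The documents give no frequency for these discontinuations, so no number of affected participants can be stated. SAP Section 4.1 records early discontinuation of the study with few participants, which limits the practical effect here. The bold and underlined marking of FDA-driven differences in Appendix 5 is not visible in the text read, so the origin of the Guillain-Barré remark cannot be judged.

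**What to change.** Add to the second group in Section 7.1.2.1: *except AEs for which Section 6.8, Section 6.9 or an Appendix 5 instruction to permanently discontinue requires or mandates discontinuation of bintrafusp alfa; these participants must not reinitiate.* Reword the Section 7.1 lead-in so that a further course is open only to participants eligible under Section 7.1.2.1.

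Because the clause names the Appendix 5 instructions, it also settles the Guillain-Barré remark. If the sponsor wants any exception to a stop, it should be named there. The sponsor should also decide whether the softer rules in Section 6.8, such as the advice to stop for recurrent Grade 3 reactions, fall under the bar.

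The cost is one clause and one rewording by amendment, with no effect on sample size, endpoints or analysis. The only loss is reinitiation for participants already under a mandatory stop.
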